## **6.1 Information to be collected on screening failures**

Patients who sign the informed consent form but fail to meet eligibility criteria during the Screening Phase will be considered screening failure and the reason will be documented on the Screening Record CRF.

## **6.2 Patient demographics/other baseline characteristics**

Data of patient demographics and baseline characteristics will be collected from all patients that include: date of birth and sex. Relevant medical history/current medical condition data includes data until the start of study drug. If there is, concomitant diseases will be recorded. In addition, MS history and MS treatment will be recorded.

At screening, an ECG will be performed to ensure that the patients continue to meet inclusion criteria. Also an ECG will be performed prior to taking the first dose of fingolimod and after 6 hours of the first dose, the ECG will be repeated. Should any of the cardiac exclusion criteria is met based on the ECG results, the patient will not be allowed to participate in the study. ECGs will be printed out and will be kept at the study site as a source document.

## **6.3 Treatment exposure and compliance**

In order to collect accurate information about the study drug exposure, the following records should be maintained for each patient: records of study medication dispensed and returned, dosages administered and intervals between visits.

Compliance will be assessed by the investigator and/or study personnel at each visit using capsule counts and information provided by the patient. A monitor will perform and document drug accountability during site visits and at the end of the study.

Patients who discontinue study medication consecutively for 1 month will be considered withdrawn.

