#### **5.4.8 Prohibited Treatment**

Use of the following treatments is NOT allowed concomitantly with the study drug during the course of the study: (use can only be considered if the study drug is permanently discontinued):

- Immunosuppressive medication (e.g. cyclosporine, azathioprine, methotrexate, cyclophosphamide, mitoxantrone, cladribine);
- Other concomitant medications: immunoglobulins, monoclonal antibodies (including natalizumab), INF- $\beta$ , glatiramer acetate, adrenocorticotrophic hormone (ACTH). The administration of any live or live attenuated vaccines (including for measles) is prohibited while patients are receiving study drug and for 3 months after study drug discontinuation. They may be administered, thereafter, once there is confirmation that lymphocyte counts are in the laboratory normal range. Use of the following treatments is allowed to manage potential adverse reactions associated with the study drug:
  - i. anticholinergics (atropine s.c. or i.v.) for treatment of symptomatic bradycardia as the first line treatment, up to 3 mg/day;
  - ii. beta-agonists/sympathomimetics (dopamine drip 5-20 $\mu$ g/kg/min or epinephrine drip 2- 10  $\mu$ g/min) for treatment of non-responsive bradycardia. Standard short course of corticosteroids (methylprednisolone i.v.) is allowed for treatment of relapses.

The medications allowed for treatment of adverse reactions and relapses are not considered study supplies, and therefore, need to be supplied by the study site. The investigator should instruct the patient to notify the study site about any new medications he/she takes after the start of the study drug.

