#### **5.4.9 Discontinuation of study treatment and premature patient withdrawal**

Patients may voluntarily withdraw from the study for any reason at any time. They may be considered withdrawn if they state an intention to withdraw, fail to return for visits, or become lost to follow-up for any other reason.

If premature withdrawal occurs for any reason, the investigator must make every effort to determine the primary reason for a patient's premature withdrawal from the study and record this information on the Study Completion CRF

The investigator should discontinue study treatment for a given patient or withdraw the patient from study if, on balance, he/she believes that continuation would be detrimental to the patient's well-being.

Study drug must be discontinued for a given patient if the investigator determines that continuing it would result in a significant risk for that patient. The following conditions/events may be considered sufficient to support a decision about the study drug discontinuation in individual cases:

- serious adverse event (e.g. cardiac failure, diagnosed malignancy)
- abnormal laboratory value(s) including liver function tests or abnormal test result(s) (e.g. PFTs, MRI and ophthalmic findings). See below and Appendix 7 and 8 for guidance for safety monitoring
- withdrawal of consent (eg., in case the patient does not consent to continue in the study after a confirmed relapse or disability progression)
- pregnancy

- use of prohibited medications, listed in Section 5.1 and 6.6.5
- adverse events
- protocol violation
- unsatisfactory therapeutic effect
- patient's condition no longer requires study treatment
- administrative problems (e.g. patient's non-compliance)

In addition, the following conditions based on the Guidance on safety and ophthalmic monitoring should result in study drug discontinuation:

- Hepatic Increase in ALT > 5 x ULN Increase in AST > 5 x ULN
- New neurological symptoms accompanied by MRI findings unexpected for MS
- Diagnosis of macular edema
- Decrease in visual acuity with abnormal OCT (increase in central foveal thickness of > 20% compared to screening or cystic changes in the macula).

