Patients who discontinue study drug should not be considered withdrawn from the study, unless one of the conditions listed above have been met. The sponsor should be notified about any decision regarding discontinuation of the study medication. Patients who discontinue the study drug should be treated according to the best standard of care. In addition to scheduled visits, patients who discontinue study drug due to adverse events or abnormalities on safety monitoring tests must be followed up with additional visits as needed in order to confirm the resolution of abnormalities. A Study Drug Discontinuation CRF should be completed, giving the date and primary reason for stopping the study drug.

For patients who are lost to follow-up (i.e. those patients whose status is unclear because they fail to appear for study visits without stating an intention to withdraw), the investigator should show "due diligence" by documenting in the source documents steps taken to contact the patient, e.g. dates of telephone calls, registered letters, etc.

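### The primary BICAMS analysis has no method for missing scores, its omnibus test in standard form needs all three time points, and the withdrawal wording leaves off-drug testing unsettled

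*Combined protocol and SAP*

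**What the plan says.** **Analysis.** Section 9.4.3.2 compares SDMT, CVLT2 and BVMTR at baseline, Month 12 and Month 24 by repeated-measures ANOVA, or by Friedman if non-normal. Post-hoc tests are Tukey, or Wilcoxon signed rank after Friedman. Section 9.1 takes all RRMS patients as the analysis set and gives no rule for incomplete data. Section 9.4.3.1 reports the non-missing n for each variable and leaves missing responses out of percentages; it says nothing else about missing data. Section 9.4.4 marks supportive analyses as not applicable. Section 6.4.1 schedules cognitive tests at baseline and Months 6, 12 and 24, so Month 6 is collected but does not enter the primary comparison.

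**Follow-up after stopping drug.** Section 6.3 states: "Patients who discontinue study medication consecutively for 1 month will be considered withdrawn". Section 5.4.9 states: "Patients who discontinue study drug should not be considered withdrawn from the study, unless one of the conditions listed above have been met". It continues: "In addition to scheduled visits, patients who discontinue study drug due to adverse events or abnormalities on safety monitoring tests must be followed up". The conditions above that sentence are mostly reasons that "may be considered sufficient to support a decision about the study drug discontinuation in individual cases", and they include "unsatisfactory therapeutic effect". The glossary defines premature withdrawal as leaving the study before treatment and all assessments are complete, and says that stopping treatment may or may not coincide with it.

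**Recording.** For premature withdrawal the investigator must determine the primary reason and "record this information on the Study Completion CRF". For stopping drug there is a separate form "giving the date and primary reason for stopping the study drug".

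**The concern.** The patients whom the plan says it analyses and those whom the named test can use may differ, and the plan does not say how the difference is handled. A patient with baseline and Month 24 scores who missed Month 12 drops out of the omnibus test in its standard form.

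This matters more than usual because the study has one arm (section 3.3), so no control group shares the loss. The hypothesis is improvement (section 9.4.3). If patients who worsen leave, those who remain look better, which is the direction of the hypothesis. The protocol itself provides a route: lack of effect is a listed reason for stopping drug, and whether stopping drug ends cognitive testing is the question the withdrawal wording leaves open. Sites could answer it differently and create avoidable missing scores.

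**Working it through.** **1. The plan's own figures (section 9.6).** The plan gives 73 patients, 10% loss and 80 enrolled.
- 73 × 1.10 = 80.3, so 80 is reproduced. Dividing instead gives 73 / 0.90 = 81.1, so 82.
- 73 is reproduced by z² p(1−p) / d² = 3.8415 × 0.0475 / 0.0025 = 72.99, with p = 0.05 and half-width d = 0.05. The half-width is my assumption; the section states none.
- Expected with follow-up: 80 × 0.90 = 72.

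**2. Who enters the test.** Suppose a share m also misses each of the Month 12 and Month 24 tests, independently (assumed). Complete triples number 80 × 0.90 × (1−m)². Baseline–Month 24 pairs number 80 × 0.90 × (1−m).

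| m | triples | pairs |
|---|---|---|
| 0 | 72.0 | 72.0 |
| 3% | 67.7 | 69.8 |
| 5% | 65.0 | 68.4 |
| 10% | 58.3 | 64.8 |

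**3. Completer bias.** Let p be the share lost, C the mean change in completers and L the mean change in those lost. The full mean is (1−p)C + pL, so the bias is C − [(1−p)C + pL] = p(C − L). The documents give no SD, correlation or dropout pattern, so the gap C − L is assumed. At p = 0.10:
- gap 3: 0.10 × 3 = +0.3 SDMT points
- gap 6: 0.10 × 6 = +0.6
- gap 0: 0
- gap −3: −0.3

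The target is 3 points (section 9.4.1). If loss were 20% or 30% (assumed), a 3-point gap would give +0.6 or +0.9.

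**4. What a mixed model recovers.** Assume SD 10, correlation 0.8 between all visits, 10% missing at Month 24 only, and one log-odds of loss per SD of change. These results come from numerical integration under a multivariate normal distribution.
- Loss depends on the observed Month 12 change: completer bias +0.29, model bias 0.
- Loss depends on the unobserved Month 24 change: completer bias +0.574, model bias +0.385. The share removed is (0.574 − 0.385) / 0.574 = 33%. The implied gap is 0.574 / 0.10 = 5.7 points.

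Over SD 8 to 12 and correlation 0.6 to 0.9, unobserved loss gives completers +0.33 to +0.97 and the model +0.22 to +0.64.

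**5. How far a sensitivity analysis must reach.** On the same assumptions the SD of change is 10 × √(2 × 0.2) = 6.32 and the SE is 6.32 / √72 = 0.745. For a 3-point change the 95% CI is 3 ± 1.96 × 0.745, or about 1.5 to 4.5. Making the missing 10% worse by delta moves the mean to 3 − 0.10 × delta: 2.7 at delta 3 and 2.4 at delta 6. With the variance held fixed, the interval reaches zero near delta = 1.54 / 0.10, or about 15 points.

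**6. The withdrawal wording side by side.** Section 6.3 makes one month off drug a withdrawal, which by the glossary means leaving before all assessments are complete. Section 5.4.9 makes staying in the study the default, with an exception.
- *Wide reading:* the exception covers the whole list. Most patients who stop drug are then withdrawn, and the two sections largely agree. This sits awkwardly with the mention of scheduled visits for patients stopping because of adverse events, since adverse events are on the list.
- *Narrow reading:* the exception covers only actual exit, such as withdrawn consent. Most patients who stop drug then stay in the study, and section 6.3 conflicts.

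The glossary allows either reading. None of the texts says whether BICAMS continues off drug or whether such scores are analysed.

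**The case against.** The strongest case on the other side has four parts.

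- **The complete-case point is partial.** Sections 9.4.1 and 9.6 frame the endpoint as baseline against Month 24, and the post-hoc Wilcoxon pairs could keep patients who miss only Month 12. That is right as far as it goes, but the plan does not say that available pairs will be used, and pairs do not help a patient with no Month 24 score. How the named software treats incomplete rows cannot be checked from the documents.
- **Section 5.4.9 leans towards continued testing.** Staying in the study is the default there, and scheduled visits carry the BICAMS in Table 6-1. This stands for patients who stop because of adverse events or safety tests. It does not settle other cases, and section 6.3 remains to be reconciled.
- **The effect is small and assumed.** This stands. The larger simulated figures need large gaps, and on the step 5 assumptions delta must reach about 15 points to undo a 3-point gain. The margin is thinner if there is no true change: a bias of 0.57 is 0.57 / 0.745 = 0.77 standard errors, which raises two-sided rejection from 5% to about 12%.
- **A new primary model is more than the gap requires.** A stated rule for incomplete patients plus a sensitivity analysis would close the gap in wording. The mixed model is still better, because it uses partial records and Month 6 scores already being collected.

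The plan also deserves credit for reporting the non-missing n and recording reasons for stopping. Those show how much loss occurred and why, but not how far it could move the result.

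**Conclusion.** The concern holds as a gap in specification that should be fixed. The primary analysis states no method for missing continuous scores, its omnibus test in standard form uses only complete triples, and no planned analysis tests the effect of loss. The likely size at the plan's 10% loss is modest: 0.3 of a 3-point target for an assumed 3-point gap, with the sign depending on who leaves.

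The documents do not support three stronger readings that a reader might infer:
- *That the result will be biased upward.* No dropout pattern is given. The bias is zero if loss is unrelated to outcome and downward if improvers leave.
- *That sections 6.3 and 5.4.9 flatly contradict each other, or that off-drug patients will go untested.* They conflict only on the narrow reading, and scheduled visits are mentioned for some patients off drug.
- *That 72 expected completers against a minimum of 73 is a failure of sample size.* The difference is one patient, and section 9.6 sets power aside.

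Confidence is medium. The textual findings are firm; every bias figure rests on assumed inputs.

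**What to change.** 1. **Primary analysis.** Replace the ANOVA/Friedman comparison with a likelihood-based repeated-measures mixed model, with visit as a factor and unstructured covariance, on all observed baseline, Month 6, Month 12 and Month 24 scores. Fit it separately to SDMT, CVLT2 and BVMTR. Keep the Month 12 comparison and report Month 24 minus baseline with its 95% CI. The model removes bias from loss that depends on observed scores, and only part of it otherwise.
2. **Sensitivity analysis.** Add one delta-adjusted analysis for patients without a Month 24 score. Extend delta until the confidence interval includes zero and report that value. A grid stopping at 6 points could end well short of it.
3. **Withdrawal wording.** Reconcile sections 6.3 and 5.4.9 with the glossary; the rule itself is the sponsor's choice. Then state whether scheduled BICAMS continues off drug, and whether those scores enter the primary analysis or only a sensitivity analysis.

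**Cost.** Sections 9.4.3.1, 9.4.3.2 and 9.4.4 need edits, with a short protocol clarification and possibly other software. No visit is added. Off-drug scores may reflect other therapies, since section 5.4.8 says of prohibited treatments that their "use can only be considered if the study drug is permanently discontinued"; the size and direction of that effect are unknown. Leaving those scores out means more missing Month 24 values and more reliance on the model and the delta analysis.

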## 6.4 Efficacy

### 6.4.1 Cognitive Tests

The Brief International Cognitive Assessment for Multiple Sclerosis (BICAMS) Battery test is the primary efficacy assessment criteria. Cognitive tests will be performed to RRMS patients at baseline and at months 6, 12 and 24 at the study center.

#### The Brief International Cognitive Assessment for MS (BICAMS)

The Brief International Cognitive Assessment for MS (BICAMS Battery) includes 3 cognitive tests, 1-Symbol Digit Modalities Test (SDMT), 2-the second edition of the California Verbal Learning Test (CVLT2) and 3-the revised Brief Visuospatial Memory Test (BVMTR).

**Symbol Digit Modalities Test (SDMT)** will be used as the test of information processing speed. It can be completed in 5 minutes for each patient including instructions, practice and testing. It's a highly efficient tool in determination of cognitive impairment in MS patients with a sensitivity rate of 82% and specificity rate of 60%. During the SDMT a series of nine symbols, each paired with a single digit in a key at the top of a standard sheet of paper similar to the one presented below is shown to the patients and patients are asked to voice the digit associated with each symbol as rapidly as possible for 90 seconds for the rest of the figures.

≥	±	«	Π	Ж	ψ	Δ	o	↑
1	2	3	4	5	6	7	8	9

ψ	±	«	Π	ψ	Δ	↑	Ж	±

ψ	«	Ж	±	Δ	↑	«	ψ	Π

[figure not shown]
**California Verbal Learning Test 2 (CVLT2)** is an auditory/verbal learning test and it begins with the examiner reading a list of 16 words. Patients listen to the list and report as many of the items as possible. There is no instruction as to the order in which items are recalled. After recall is recorded, the entire list is read again followed by a second attempt at recall.

Altogether, there are five learning trials. After 25 min there is a delayed recall trial as well as a yes/no recognition memory task. The 16-item list (an example is given below) will have words that conform to four semantic categories, in this case sports, vegetables, clothes, and tools. Some subjects will recall items in a grouped fashion, and others may recall the list in serial order. There are many variables of recall available in the CVLT2, as a second list is presented, and after 25 min there is a delayed recall trial as well as a yes/no recognition memory task. The list will be read aloud five times in the same order to the patient, at a slightly slower rate than one item per second. Patients will be required to recall as many items as possible, in any order, after each reading of the list. The CVLT-II can be completed in 5–10 minutes, including instructions, testing and responses. The CVLT-II (T1-5 version) has been

validated with brain MR total lesion area and right superior frontal atrophy, 44 MR T1 and FLAIR lesion volume, BPF and third ventricular width and MR diffusion measures.

Football	Paper	Folder	Candy
Notebook	River	Boxing	Envelope
Island	Tennis	Mountain	Valley
Billiards	Cake	Pie	Ice cream

**Brief Visuospatial Memory Test (BVMTR)** will assess visual/spatial memory in BICAMS. In this test, six abstract designs such as the figure shown below are presented for 10 seconds. The display is removed from view and patients render the stimuli via pencil on paper manual responses. Each design receives from 0 to 2 points representing accuracy and location. Thus, scores range from 0 to 12. There will be three learning trials, and the primary outcome measure is the total number of points earned over the three learning trials. Because there is little evidence that the delayed recall trial adds to discriminant validity in MS, as in the MATRICS consensus battery, only the initial learning trials will be included for BICAMS.

**Paced Auditory Serial Addition Test ( PASAT)**

The Paced Auditory Serial Addition Test (PASAT) has been widely used in MS trials and is viewed as one of the most adequate measures of cognitive dysfunction in multiple sclerosis. PASAT was introduced by Gronwall in the 1970s as a clinical tool for measuring the severity of brain injury and its recovery. This test is considered to be a measure of sustained attention, divided attention, concentration, and information processing speed.

During the test the participant is asked to listen to a recorded series of single digits (from 1 to 9) and add each number to the one presented previously under a considerably time pressure. MS patients have been found to be impaired compared with healthy controls at the rapid rates (1.2 and 1.6 sec), at the slow rates (2.0 and 2.4 sec), or at all of the rates of presentation. In the Multiple Sclerosis Functional Composite (MSFC) version, the presentation rate is 3.0 seconds.

The 3-minute version of the PASAT will be used in this study and the number of correct answers will be the outcome variable. PASAT will be performed to RRMS patients at baseline and at months 6, 12 and 24.

### **Stroop Test:**

The Stroop Color and Word Test assesses cognitive processing and provides valuable diagnostic information on brain dysfunction, cognition, and psychopathology. It is based on the observation that individuals can read words much faster than they can identify and name colors. It is a five minute test is applicable for those between the ages of 15 and 90.

This test was adapted from the paper-based Stroop Color-Word Interference Test (Golden, 1978) and consists of three 60-s trials, each of which was preceded by a set of eight practice items to insure the participant understood the task to follow. In the first trial (word reading, W), participants will read color words (RED, BLUE, YELLOW, GREEN) printed in black letters; in the second trial (color naming, C), they will name the colors used to print a row of four Xs; and in the third trial (color-word naming, CW), they will name the color of the print for a set of incongruent Stroop stimuli (e.g., BLUE printed with red letters). In each trial, the stimulus item appeared on the paper, the participant will respond verbally to the item, and either the experimenter (E-press condition) immediately will show the next item. The number of items completed in the allotted time will be recorded. In addition to the W, C, and CW scores, the combined score for word-reading and color-naming (W + C) might be examined as a particularly good measure of processing speed. Also, a measure of relative interference (RI) will be computed by dividing the difference between the color-naming and the color-word naming scores by the color-naming score ( $RI = \frac{C - CW}{C}$ ).

Stroop test will be performed to RRMS patients at baseline and at months 6, 12 and 24.

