#### **9.4.2 Secondary efficacy endpoints:**

The metric for the PASAT assessment is the number of correct answers.

The Stroop test yields three scores based on the number of items completed on each of the three stimulus sheets.

All MRI analysis will be performed at the Kocaeli University Faculty of Medicine which is the center of the study coordinator investigator.

SIENAX—cross-sectional method will be used to measure atrophy. (25)

Whole brain volume, total gray matter volume, cortical gray matter volume and deep gray matter volume will be measured.

White matter lesions will be segmented by using  $k$  nearest neighbor classification with tissue-type priors, The resulting lesion volume will be normalized for head size to create normalized lesion volume (26,27) Lesion filling will be applied to minimize the effect of hypointense lesions on atrophy measurements (28). Normalized whole-brain volume, normalized gray

matter volume (NGMV), and normalized white matter volume (NWMV) will be measured with SIENAX (part of FSL [Functional MRI of the Brain, or FMRIB, Software Library] 5.0.2, <http://www.fmrib.ox.ac.uk/fsl>) by using optimized parameters for brain extraction (29,30).

Deep gray matter volumes will be measured by using FSL FIRST software (31). Cortical thickness will be measured by using FreeSurfer 5.1 software (<https://surfer.nmr.mgh.harvard.edu/>) (32,33). FreeSurfer uses the T1-weighted image to locate the white matter and pial surface. The distance between both surfaces gives the cortical thickness at each location.

Thalamic and intracranial volumes will be segmented automatically. Thalamic volumes and thalamic fractions will be calculated as ratios of the left and right thalamic volume to the intracranial volume.

Correlation between effect of fingolimod on cognitive performances and brain atrophy will be explored.

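### The Stroop is scored on items completed rather than items correct, so the colour-word and interference scores can move opposite to performance when the misreading rate changes; its administration format also needs reconciling

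*Combined protocol and SAP*

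**What the plan says.** Section 6.4.1 (Stroop Test) describes a test that "consists of three 60-s trials": word reading (W), colour naming on rows of Xs (C), and naming the print colour of incongruent words (CW). On scoring it says: "The number of items completed in the allotted time will be recorded". Relative interference is RI = (C - CW)/C, and W + C may also be examined.

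Section 9.4.2 gives the same basis: "The Stroop test yields three scores based on the number of items completed on each of the three stimulus sheets".

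For PASAT, tested at the same visits, section 6.4.1 states that "the number of correct answers will be the outcome variable", and section 9.4.2 agrees: "The metric for the PASAT assessment is the number of correct answers".

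On administration, section 6.4.1 says that "either the experimenter (E-press condition) immediately will show the next item", in a sentence whose opening alternative is never completed. Section 9.4.2 instead refers to items completed "on each of the three stimulus sheets".

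Section 2.3.2 makes PASAT and Stroop at baseline, month 12 and month 24 a secondary endpoint. Section 9.4.3.2 analyses it by repeated measures ANOVA (Friedman if non-normal) and also correlates Stroop scores with MRI parameters. It does not say which of W, C, CW, W + C or RI is analysed.

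**The concern.** A count of items completed rewards speed whatever the accuracy. In the colour-word trial this matters because the characteristic wrong answer, reading the word, is also the quick one; section 6.4.1 introduces the test on exactly that premise. As the rule is written, each misread item saves time and still counts. It raises CW and lowers RI, and both changes would be read as better.

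The endpoint is change over time in a single arm. If patients trade accuracy for speed between visits, or the reverse, the score can move the wrong way, and no comparator group would show it. If errors are not recorded, the two components cannot be separated afterwards.

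The format question is separate. If the examiner presents items one at a time, the examiner's own speed enters a timed count. If the patient works down a sheet, it does not. In a multicentre study the two would not give comparable scores.

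**Working it through.** **No figure to reproduce.** The documents give no expected Stroop score, SD, error rate or effect size. The check is of direction, followed by an illustration with assumed rates.

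**Which scores are affected.** In W, reading the word is the task. C uses rows of Xs, so there is no word to misread. W, C and W + C are therefore untouched by word misreading. CW is affected, and so is RI through CW.

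**Direction.** Let W and CW be the error-free counts per 60 s, and e the share of colour-word items answered by reading the word at word-reading speed.

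- Completed = 1 / [(1 - e)/CW + e/W]. This rises with e whenever W > CW.
- Correct = completed × (1 - e) = 1 / [1/CW + (e/(1 - e))/W]. This falls as e rises.
- If each error must be corrected before moving on, so that a misread item costs the reading time plus the naming time: count = 1 / [1/CW + e/W]. This also falls as e rises.

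The opposite movement needs only W > CW, which follows from the protocol's premise.

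**Illustration.** Assumed W = 90, C = 70, CW = 40, with misread items taking pure word-reading time. For e = 0.2, time per item = 0.2 × 60/90 + 0.8 × 60/40 = 1.333 s. Completed = 60/1.333 = 45.0 and correct = 45.0 × 0.8 = 36.0. RI = (70 - 45)/70 = 0.357 on completed items and (70 - 36)/70 = 0.486 on correct items.

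| Misread share e | Completed | Correct | Errors corrected first | RI, completed | RI, correct |
|---|---|---|---|---|---|
| 0 | 40.0 | 40.0 | 40.0 | 0.429 | 0.429 |
| 0.1 | 42.4 | 38.1 | 38.3 | 0.395 | 0.455 |
| 0.2 | 45.0 | 36.0 | 36.7 | 0.357 | 0.486 |
| 0.3 | 48.0 | 33.6 | 35.3 | 0.314 | 0.520 |

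**Read as change from baseline.**

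- Misreading rises from 0 to 20%: completed +12.5% (40.0 to 45.0), correct -10% (40.0 to 36.0). A decline looks like a gain.
- Misreading falls from 20% to 10%: completed 45.0 to 42.4, correct 36.0 to 38.1. A gain looks like a decline.
- Misreading is 20% at both visits with unchanged speeds: 45.0 both times, so no spurious change.

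**Sensitivity.** With W/C/CW from 80/60/35 to 110/80/55 and e from 5% to 30%, against no errors, completed rises by 3% to 20% and correct falls by 2% to 18%. The signs were opposite in every case run.

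**Format.** Section 6.4.1 has items advanced by the experimenter; section 9.4.2 has one sheet per trial. Both cannot describe the same administration.

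**The case against.** The strongest reply is that the endpoint is change over time. An error rate that stays the same largely cancels, and nothing in the documents says that misreading will rise on treatment. That stands. A reader might infer that the rule biases the trial towards showing benefit; the documents do not support this, because falling error rates would hide a real gain.

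Second, completed may have been meant as correctly completed. The colour-word task is to name the print colour, practice items precede each trial, and the test is adapted from a published paper version whose error rules may have been assumed. The protocol does not spell out full scoring for every instrument either. This is possible, but the error rule is not written, the published version is not in the reference list, and an adapted test does not automatically carry over its source's scoring.

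Third, PASAT is paced by a recording, so a count of correct answers is natural there, and a different metric for Stroop is not in itself an inconsistency. Agreed. The contrast shows only that the plan writes correct where it means correct.

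Fourth, the format conflict rests largely on one garbled sentence that may be an editing remnant; the same paragraph also mentions items on paper, and three trials fit three sheets. A reader might infer that sites will mix formats. The documents do not show that, only that the text would permit it.

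**Conclusion.** The point holds in a conditional form. As written, the Stroop rule lets CW and RI move opposite to true performance whenever the misreading rate differs between baseline and months 12 or 24, in either direction. The direction follows from the protocol's own premise that words are read faster than colours are named. The size is unknown: the rates of 90/70/40 and the misread shares are assumptions, and hesitation or self-correction would shrink the gap.

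The reach is limited to CW and RI within a secondary endpoint, and to the MRI correlation if those scores are used there. Because section 9.4.3.2 names no Stroop score, it is not established that the tested one is affected. It would be wrong to infer that the main cognitive result is compromised: the BICAMS primary endpoint and the N of 80 do not depend on Stroop.

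The format discrepancy is a real textual conflict that needs reconciling. It is worth settling both matters before baseline testing, because errors that were not recorded cannot be recovered.

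**What to change.** - In sections 6.4.1 and 9.4.2, define W, C and CW as the number of correct responses in 60 s. Alternatively, require each error to be corrected before the next item counts. Either rule removes the reversal.
- Record the number of errors per trial on the CRF.
- Compute RI from the redefined scores and state that a lower RI is better.
- In section 9.4.3.2, name the Stroop score or scores to be analysed over time and correlated with MRI.
- Reconcile the experimenter-advanced description in section 6.4.1 with the three sheets in section 9.4.2, and use one format at all sites and visits.

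The cost is protocol wording and an error-count field on the CRF, with no extra visit or test session. The downside is that examiners must mark errors while timing.
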